Objectives	
Aim 1: To conduct a pilot evaluation to assess the feasibility and acceptability of a patient-centered, web-based navigation tool, ConnectedCancerCare, that supports the transition from breast cancer treatment to survivorship and promotes team-based survivorship care.
 
Aim 1A: To assess the feasibility of recruiting at least 60 and up to 70 women with early-stage breast cancer who are completing primary treatment in the breast oncology clinic to the study.
 
Aim 2A: To assess the acceptability of the CCC website among the 30 women randomized to the CCC intervention group.
 
Aim 2: To explore whether CCC influences patient and provider communication about team-based survivorship care, patient-reported knowledge about team-based survivorship care and follow-up visit scheduling in primary care.
 
Aim 3: To conduct debriefing interviews with participating patients and providers in the intervention group to inform the future evaluation and implementation of the tool.

Study Design	Pilot randomized control trial
Eligibility Criteria	
1. Ability to voluntarily provide written IRB-approved informed consent and communicate satisfactorily with the investigator, to participate fully in the study, and comply with all its requirements.2. Women diagnosed with Stages 0-II breast cancer

	3. Women who are receiving care from a medical oncologist 4. Women who are completing their primary treatment for breast cancer and transitioning into survivorship
Statistical Considerations	As this is a pilot study, we will be primarily assessing whether the recruitment of at least 60 and up to 70 women is feasible, and whether the majority of participants (50%) report the tool is acceptable using descriptive statistics. We will assess differences in patient-reported outcomes between the intervention group and control group, but this is an exploratory analysis to guide future versions of the tool and our planned multi-site RCT. As such, a sample size of at least 60 women and up to 70 participants is sufficient to address our primary outcomes (see power calculation section).
Number of Participants	At least 60 and up to 70 women (30-35 intervention and 30-35 control arm)
Estimated Enrollment Period	9 months
Estimated Study Duration	12 months

1. Objectives/Specific Aims

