Aim 1A: To assess the feasibility of recruiting at least 60 and up to 70 women with early-stage breast cancer who are completing primary treatment in the breast oncology clinic to the study. We will randomize 30-35 women into the intervention group who will view the CCC website and 30-35 women into the control group, who will view an online care plan document. **H1a:** It will be feasible to deploy CCC in an academic breast clinic, as measured by the successful recruitment of at least 60 and up to 70 women (80%) into the study.

Aim 1B: We will assess the acceptability of the CCC website among the 30-35 women randomized to the CCC intervention group. **H1b:** CCC will demonstrate high usability among those who interact with it, as measured by patient-reported ratings of website usability (ease of use, time to completion, amount of information), usefulness, and whether they would recommend it to others.

Aim 2: To explore whether CCC influences patient and provider communication about team-based survivorship care, patient-reported knowledge about team-based survivorship care and follow-up visit scheduling with primary care. **H2a:** Patients who view CCC will report greater knowledge about and better communication with their providers about team-based survivorship care when compared to the control group. **H2b:** A greater proportion of patients who viewed CCC will report scheduling a follow-up visit with their PCP within 3 months compared to those who viewed the control website.

Aim 3: To conduct debriefing interviews with a sample of patients and their providers about their experiences with *ConnectedCancerCare*. We will debrief oncologists, PCPs and patients (in the intervention arm) about the usefulness of the tool and how to best implement it into practice. The results will then be used to further tailor and revise the tool and develop future evaluation plans, as well as guide post-evaluation implementation and ultimate incorporation into the electronic medical record.

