4.3. Subject Selection

After completion of the baseline questionnaire, participants will be randomized to either enter the *ConnectedCancerCare* website (n=30-35), or a static website (n=30-35) which contains a brief survivorship care plan template in PDF format (see Appendix). We will employ block randomization, with a block size of 6 (10-12 blocks total) to ensure that the study group assignments are equally distributed throughout recruitment.

[figure not shown]
[figure not shown]

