We will collect patient-reported outcomes in both the intervention and control groups. We will then explore whether the intervention (compared to control) is correlated with the following measures: Knowledge about continuing care guidelines measured by items used in our previous studies adapted to continuing care (categorical);²⁷ Preferences for team-based care (PCP or oncologist); Satisfaction with care measured by a care coordination question used in previous CanSORT studies tailored to the timing of transition (categorical);⁴⁰ Communication with providers about continuing care measured by an item from the SPARCCS adapted to the patient perspective (categorical).^{18,25} We will explore follow-up visit scheduling (yes/no) using patient-reported measure of whether or not they have scheduled a visit with their PCP since viewing the tool (or control). We will also ask patients whether they have seen their oncologist (yes/no) since viewing the tool and verify their responses using MiChart data.

Aim 3: Debriefing interviews

Guiding questions with prompts will be used to obtain patient and provider feedback (See Appendix for draft interview guide). Patients will be asked about the content of the tool, how they used the tool (or not), and whether it improved their care transition experience. In addition to these questions, providers will also be asked about their experience with the tool summary, how well it fit into their clinical practice, with the goal of understanding how to best imbed the tool into current clinical work-flow.

6. Procedures

6.1. Data Management: We use established human subjects' protection protocols that address the limited use of personal health information, transfer of de-identified datasets within our

institution, storage of information from various data sources and surveillance and response to adverse events. The primary risks of the study are related to breaches in confidentiality and patient concerns about the use of their medical information. We have a long track record of employing the highest standards of patient confidentiality. However, we will respond promptly to any patients or providers who contact the staff or investigators about any concerns related to the study.

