We will then explore comparing knowledge, satisfaction, communication and utilization among the 30-35 women who engaged with the tool to the 30-35 who received the standard of care using chi-square tests and two-sided student t-tests where appropriate. This is designed to be a pilot study to determine if patients who engage with tool score higher on key knowledge, communication, and satisfaction items compared to those who received the control.

Aim 3: Patient and Provider Debriefing Interviews

To better understand what worked and did not work following the pilot testing and the underlying mechanisms of the intervention, we will conduct a formative assessment with both patients and

providers who had a patient who enrolled in the study. All interviews will be audio recorded and transcribed and analyzed using Dedoose and NVivo software. The investigator team will review the transcripts to identify overall themes which will help to refine the tool as needed and guide the future implementation of it into a broader system-level tool used in clinical practice.

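### Does the Aim 2 analysis compare only women who used the website, rather than the randomised arms?

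*Combined protocol and SAP*

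**What the plan says.** Section 7 (Data Analysis Plan, Aim 2) describes the comparison of knowledge, satisfaction, communication and utilisation as one "among the 30-35 women who engaged with the tool to the 30-35 who received the standard of care", by chi-square and two-sided t-tests. Its next sentence gives the purpose as to "determine if patients who engage with tool score higher on key knowledge, communication, and satisfaction items compared to those who received the control".

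The hypotheses in section 1 use viewing language. H2a reads "Patients who view CCC will report greater knowledge about and better communication with their providers" and takes the control group as comparator. H2b concerns "scheduling a follow-up visit with their PCP within 3 months compared to those who viewed the control website".

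Other places name the groups by assignment:

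- Study Summary, Statistical Considerations: "We will assess differences in patient-reported outcomes between the intervention group and control group".
- Section 5 (Measures, Aim 2): the aim is to "explore whether the intervention (compared to control) is correlated with the following measures", with outcomes collected in both groups.
- Section 1, Aim 1A: "We will randomize 30-35 women into the intervention group who will view the CCC website", with the same number randomised to the control group.
- Section 4.3: "After completion of the baseline questionnaire, participants will be randomized to either enter the" intervention site or the static control site, 30-35 in each.

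No section uses the term intention-to-treat or names an analysis set, and none defines engagement.

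**The concern.** Engagement happens after randomisation. If the intervention side were limited to women who used the site while the control side stayed whole, the groups would no longer be comparable by design. Women who engage with a survivorship website may also be those more inclined to learn about follow-up care or book a primary care visit, so part of any difference would reflect who they are. The error could go either way.

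The means to form such a subset exist, because section 5 records page views and time on the website. Section 5 also allows, in the debriefing interviews, that a patient may not have used the tool. At stake are the exploratory Aim 2 contrasts, which the Study Summary says will guide later versions of the tool and the planned multi-site trial.

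**Working it through.** **The plan's own figure.** The documents state no power, effect size or significance level for Aim 2. The one precision figure (section 7.1) is for acceptability: a 95% interval of width 0.374 at n = 30 and 50%. The exact Clopper-Pearson interval for 15/30 runs from 0.313 to 0.687, width 0.374, so it reproduces. It does not depend on the Aim 2 wording.

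**What the text implies.**

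1. The count. Sections 1 and 4.3 randomise 30-35 women per arm, and section 7 compares 30-35 with 30-35. A user-only group of that size needs all, or nearly all, of the arm to be users, and then the two readings almost coincide. At 80% use the group would be 0.8 × 30 = 24 to 0.8 × 35 = 28, which is not what section 7 says.
2. The vocabulary. Aim 1A treats viewing as what happens to everyone randomised to the intervention. H2a sets women who view the tool against the control group, so viewing stands in for assignment.
3. The procedures. Consent and the baseline survey are completed on the website (sections 4.2 and 4.4.4), site entry follows randomisation (sections 4.3 and 4.5), and the 3-month survey is reached by logging in again (section 4.4.3). Every woman with Aim 2 follow-up data has therefore logged in on at least two occasions. That is not proof of engagement, but it leaves little room for complete non-use among those analysed.
4. The use data. Sections 5 and 7 plan page views and time on site only as averages, under feasibility. Nothing links them to Aim 2 or sets a threshold.

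**Size if the literal reading were followed.** The non-use share and the outcome gap are assumptions; the documents give neither. Let e be the share of the intervention arm who are users and g the user-minus-non-user difference in the outcome proportion. With no true effect and only the intervention side filtered, bias = (1 − e) × g.

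| Non-use (1 − e) | g = ±10 points | g = ±20 points | g = ±40 points |
|---|---|---|---|
| 10% | ±1 | ±2 | ±4 |
| 20% | ±2 | ±4 | ±8 |
| 30% | ±3 | ±6 | ±12 |

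The 95% half-width for a difference in proportions near 50% is 1.96 × √(0.25/n₁ + 0.25/n₂):

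- 30 v 30: 1.96 × √0.01667 = 0.253
- 35 v 35: 1.96 × √0.01429 = 0.234
- 24 v 30: 1.96 × √0.01875 = 0.268

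The false-positive rate must be compared at the same group sizes, because the chi-square test is discrete and its size moves with n. Exact binomial enumeration of the uncorrected test at a nominal 5%, overall rate 50%, gives:

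| Groups | No bias | g = 20 points |
|---|---|---|
| 30 v 30 (no filter) | 5.2% | not applicable |
| 24 v 30 (20% non-use) | 4.9% | 5.9% (54% v 50%) |
| 21 v 30 (30% non-use) | 5.3% | 7.4% (56% v 50%) |

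At the far corner, 30% non-use with a 40-point gap, the rate is about 14%. Nothing in the documents points to values that extreme.

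**The case for a change.** The strongest case for a change is that no sentence says women are analysed as assigned, and that the section an analyst will open first names the intervention side by use, twice. H1b does use interaction with the tool to describe whose usability ratings count, so the authors do not always treat use and assignment as the same thing. Section 5 dates visit scheduling from viewing the site, a starting point that a non-viewer lacks, so she could be dropped without much thought. The intervention is also wider than the website. Provider summaries (section 4.4.2) and weekly reminders to book a primary care visit (section 4.4.4) follow from assignment, so a user-only set would discard women who received components aimed at the H2b outcome. The correction would be a matter of words.

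The missing sentence and the loose wording stand as facts. They do not show that a user-only comparison is planned or likely. H1b concerns acceptability, which is measured in the intervention arm only and involves no between-arm contrast. The assignment-based summaries and reminders are a further reason for an analyst to keep the whole arm. That the alternative is not expressly excluded is true of many unstated options in a short pilot plan.

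**Conclusion.** The concern does not call for a change. Section 7 uses engaging with the tool as loose shorthand for being assigned to it. The Study Summary, section 5, the randomisation text in sections 1 and 4.3, and the matching count of 30-35 per side all point to comparison by assigned arm, which is also what a competent analyst would do by default. This is a gap in wording that changes no expected result.

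If the literal reading were followed, the bias would be 2 to 6 percentage points for a 20-point gap and 10% to 30% non-use, and zero if every woman used the site. That is well inside a half-width of 23 to 27 points, in an analysis the plan labels exploratory. These sizes rest on assumed non-use and outcome gaps, and the upper non-use values look high for women who have logged back in to answer the 3-month survey. Recruitment feasibility and acceptability are unaffected. Handling of women who do not return the 3-month survey is a separate matter and is not judged here.

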4.4. Intervention (*ConnectedCancerCare*)

Overview: The CCC tool is a personalized, navigation website that is tailored to patients' preferences for provider roles in follow-up care, their satisfaction with their current PCP, and their worry about cancer recurrence. This pilot study is designed to determine whether an informative and tailored website can assist in guiding patients to utilize team-based care for their follow-up cancer care. The tool involves a website and text-based reminder system to help patients transition from active cancer treatment to ongoing/survivorship, team-based care and includes three research phases: 1) baseline survey and 2) 3-month follow-up survey among all participants; and 3) patient/provider interviews among a sample of participants in the intervention arm to assess patients' understanding of survivorship care, usage of the website, and increased knowledge of team-based survivorship care as a result of using the tool. This tool was developed by the UM Center for Health Communications Research (CHCR) under the direction of the PI, [name], with input from oncologists, primary care physicians and other study co-investigators, and then beta tested among breast cancer patients. We believe this tool will be of benefit to patients comfortable using the internet and to clinicians who value additional information about their patients' preferences and concerns.

Development: CCC was developed using "agile development",⁴³⁻⁴⁵ which included content development and usability testing as used previously by the investigators in a trial of a patient decision aid for breast cancer treatment.²⁶ CCC was developed using an iterative, agile cycle, which included planning (content decisions), design (graphical display and media elements), development (programming) and testing (feedback from stakeholders on draft versions). Testing included an iterative process of tailoring, timing, data, and functionality. The next phase (Phase 2) includes the pilot evaluation detailed in this protocol (Figure 3).

Content: The content of the CCC navigation tool was developed by Drs. [name] and [name], along with clinical experts in the UM-RCC and CHCR. The development built upon the existing programming of the iCanDecide tool, a novel treatment decision-making tool developed by [name], which recently was evaluated in a full-scale randomized control trial with 500 patients (REF). CCC includes content focused on four areas as outlined in the conceptual model:

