
- 1) **Inform:** This section provides the patient with key facts about survivorship guidelines and what to expect from team-based care.

- 2) **Clarify:** This section provides tailored content to clarify appropriate provider roles in delivering team-based care based on their collected preferences. The preferences outlined in the questionnaire section are used to tailor the content on this page.
- 3) **Communicate:** This section promotes communication with the oncologist and PCP about this topic and includes tips and suggestions on how to communicate with their physicians and get the most out of their clinic visits.
- 4) **To do list for follow-up care and reminders:** This sections outlines for patients what services they will need during survivorship, based on clinical guidelines. Customized alerts will be sent to participants to remind them to schedule their follow-up visits with their PCP, according to the guideline-recommended schedule and to complete their follow-up survey. A total of three reminders for each event have been built into the website program, and subjects are given the choice of how they want to receive reminders (i.e. text or email). Currently, the ConnectedCancerCare website is not linked to MiChart; however, that is a desired feature for future development.

Screen shots of the website content and information on how to access the website directly are included in Appendices 5.

4.4.1. Baseline Questionnaire: After completing the online consent, patients will begin the online questionnaire which collects information that is used to tailor the content of the website. The survey is included in the Appendix. Measures used to tailor the website content include the following:

- a. Knowledge of guidelines for breast cancer follow-up screening and preventive care
- b. Current PCP (yes/no)
- c. Preferences for providers in team-based (PCP or oncologist)
- d. Satisfaction with care coordination at the time of transition
- e. Communication with providers about continuing care
- f. Worry about recurrence

We will also ask patients to provide the contact information for their medical oncologist and primary care physician as part of the baseline questionnaire, which will be used to fax a provider summary to both physicians' offices. The research coordinator will then verify this contact information using MiChart and the internet (for address verification) as needed.

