4.5. Time and Events Table

Study Events	Pre-study (after completing primary treatment)	Time 1 (When viewing the website initially)	Time 2 3 months post-baseline questionnaire completion)	Time 3 1-3 months post-follow-up questionnaire completion)
Informed Consent	X			
Baseline Questionnaire	X			
Randomization		X		
View intervention or control website		X		
Follow-up questionnaire			X	
Debriefing Interviews				X

5. Measures

The measures described in detail below were selected after literature review, and were directly informed by our conceptual model and the results of our prior work and pilot data. The measures are described by specific aim below:

Aim 1A: Feasibility

Feasibility will be defined by the successful recruitment of at least 60 women with half randomized to the intervention website and half to the control website over a 9-month time period. Based upon positive response rates of patients in previous studies of survivorship interventions and the iCanDecide pilot trial, we anticipate approaching approximately 87 women in order to achieve a similar response rate of 80% enrollment (n=70). We will also assess the proportion of those successfully recruited who complete the baseline survey and the follow-up survey. In addition, we will capture paradata including participants' average number of page views, and average time on website.

Aim 1B: Acceptability

Acceptability and usability will be defined by asking participants in the intervention arm to rate their experiences with the tool on 5 point Likert-type scales, as follows: (1) CCC was easy to use, (2) CCC was helpful during my transition to survivorship, (3) CCC helped me think about when to see my PCP and when to see my oncologist, (4) I would recommend CCC to other patients, (5) The time it took to go through the website (6) The amount of info.

Based on our prior work, we will use a cut off of 50% of more reporting a score above 3 as acceptable within that domain. We will also examine the distributions within each domain and determine how we can make the next versions of the tool more acceptable to patients as needed. We will then create a summary score of acceptability by averaging the responses to the 6 items, with a score of 3 or more indicating the tool was acceptable to the majority of patients.

Aim 2: Exploratory patient-reported outcomes

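### Aim 2 compares the arms without using the baseline values of the same three constructs; adjusting for them costs almost nothing and usually brings a modest gain in precision

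*Combined protocol and SAP*

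**What the plan says.** - **Analysis (Section 7, Aim 2).** Knowledge, satisfaction, communication and utilization are compared between arms of 30-35 women "using chi-square tests and two-sided student t-tests where appropriate". No covariate, regression model or change score is named for Aim 2 anywhere.
- **Order of events (Section 4.3).** "After completion of the baseline questionnaire, participants will be randomized to either enter" one of the two websites. The events table in Section 4.5 agrees.
- **Baseline content (Section 4.4.1).** Under the lead-in "Measures used to tailor the website content include the following", the list includes "Knowledge of guidelines for breast cancer follow-up screening and preventive care", "Satisfaction with care coordination at the time of transition" and "Communication with providers about continuing care".
- **Follow-up.** The Section 4.4 overview describes a "3-month follow-up survey among all participants", and Section 4.4.3 sends it to both groups. Section 5, Aim 2, names knowledge, satisfaction (a care-coordination question) and communication as outcomes in both arms, each labelled categorical.
- **Status.** The Study Summary (Statistical Considerations) calls the between-arm comparison exploratory and says it will guide later versions of the tool and the planned multi-site trial.

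**The concern.** Each randomised woman should already have a pre-randomisation value for three of the Aim 2 constructs. A two-group test on the 3-month values discards that information. Randomisation keeps the test valid, so the loss is precision and not type I error.

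It deserves a line in the plan because Aim 2 is meant to inform a larger trial, and the estimated arm differences and their uncertainty are the natural product of a pilot comparison. At 30 per arm, unadjusted power for an assumed moderate effect is below 50% whichever response format is assumed, so a cheap gain is useful. Recruitment and acceptability, the primary aims, are unaffected. Scheduling of a PCP visit has no baseline counterpart and is outside this point.

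**Working it through.** **The plan's own figure.** The only precision figure is in Section 7.1: a 95% interval of width 0.374 for a proportion of 50% with n = 30. The exact (Clopper-Pearson) interval for 15/30 is 0.313 to 0.687, width 0.374, so it reproduces. It concerns acceptability. Nothing comparable is given for Aim 2.

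**Inputs.** From the documents: 1:1 allocation, 30-35 per arm, two-sided tests, categorical outcomes. Assumed, because the documents do not give them: 5% significance level, baseline-to-follow-up correlation (0 to 0.7), number of categories, marginal split, a true shift of 0.5 SD, and 24 completers per arm as a 20% loss case.

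**Step 1: formula for a continuous score.** With n per arm and observed correlation ρ, the adjusted variance relative to the unadjusted variance is (1 − ρ²) × (1 + 1/(2n − 4)). The second factor is the price of chance baseline imbalance. For n = 30 it is 1 + 1/56 = 1.018.

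| ρ | Variance ratio | SE change | Equivalent n per arm (30 / ratio) |
|---|---|---|---|
| 0 | 1.018 | +0.9% | 29.5 |
| 0.3 | 0.91 × 1.018 = 0.926 | −4% | 32 |
| 0.5 | 0.75 × 1.018 = 0.763 | −13% | 39 |
| 0.7 | 0.51 × 1.018 = 0.519 | −28% | 58 |

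The difference detectable with 80% power falls from 0.74 SD to 0.71, 0.64 and 0.53 SD at ρ = 0.3, 0.5 and 0.7.

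**Step 2: categorical items.** Coarse categories weaken the observed correlation, so the gain is smaller. The simulation used 40,000 trials per cell and a bivariate normal latent variable with correlation r, cut into 5 or 3 equally likely levels or into two. The unadjusted analysis is a pooled t-test on the score; the adjusted one is a linear regression on arm and baseline. Results for 30 per arm with complete follow-up, at r = 0.3 / 0.5 / 0.7:

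| Item | SE reduction | Equivalent n per arm | Power at 0.5 SD shift: unadjusted, then adjusted |
|---|---|---|---|
| 5 categories | 3 / 10 / 22% | 32 / 37 / 50 | 43-44%, then 46 / 51 / 63% |
| 3 categories | 2 / 8 / 18% | 31 / 35 / 45 | 39-40%, then 41 / 45 / 54% |
| Yes/no, 50:50 | 1 / 5 / 12% | 31 / 33 / 38 | 32-33%, then 34 / 35 / 40% |
| Yes/no, 80% favourable | 1 / 4 / 10% | – | 23%, then 22 / 23 / 25% |
| Yes/no, 20% favourable | 1 / 4 / 10% | – | 30%, then 30 / 32 / 35% |

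At r = 0 the standard error rises by about 1%. Type I error at 30 per arm was 4.8-5.2% unadjusted and 4.7-5.2% adjusted.

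**Step 3: the two approaches agree.** For an evenly split binary item, latent r = 0.5 gives an observed correlation of (2/π) × arcsin(0.5) = 0.333. Step 1 then gives √[(1 − 0.111) × 1.018] = 0.951, a 5% reduction, as simulated. Correlations quoted on the observed scale therefore show larger gains than the same number on the latent scale.

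**Step 4: other sizes.** The ratios at 24 and 35 per arm agree with those at 30 to within about 0.01. With 24 completers per arm, power goes from 36% to 38 / 42 / 54% (5 categories), 33% to 34 / 37 / 44% (3 categories) and 29% to 28 / 29 / 33% (50:50). In that last case the unadjusted test runs at 5.8-6.0% because of discreteness, which slightly hides the gain. With 35 per arm, power for 5 categories goes from 49% to 51 / 57 / 71%.

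**Step 5: chance imbalance is not a second argument.** At 30 per arm, 34% of trials have a baseline difference above 0.25 SD on a 5-category item. At r = 0.7 the unadjusted false-positive rate is 11.4% in those trials and 1.8% in the rest: 0.34 × 11.4 + 0.66 × 1.8 = 5.1% overall. This is the precision loss seen from another side.

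**The case against.** **It is a preference, not an error.** That stands. The tests are valid, the aim is exploratory and nothing in Section 7 forbids adjustment. How the pilot results will be used is also only sketched: no section says that Aim 2 will size the later trial.

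**Item matching is unseen.** This stands as a limit. Section 4.4.1 lists tailoring topics, two of the three outcomes are single items, and both surveys are in an appendix that was not available. The overlap is at the level of constructs, so the change must be conditional on matching items.

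**The gain may be smaller than modelled.** Baseline answers tailor the intervention site and feed the provider summary, so the correlation could be lower in that arm. With an assumed r of 0.5 in control and 0.2 in intervention, a 0.5 SD shift and 30 per arm, the standard error falls by about 4% (5 categories), 3% (3 categories) and 2% (binary), against about 10, 7 and 5% with equal correlations. That is still a gain, at the low end of the range above. In a few binary cells power does not rise at all.

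**The planned test for a categorical item may be chi-square, not t.** At a 0.5 SD shift, chi-square power is about 25% (5 categories) and 30% (3 categories), against 44% and 39% for the t-test on scores. For ordered items, scoring therefore matters more than adjustment at r = 0.3 to 0.5. This stands, and the sponsor should state the coding. Section 7 itself speaks of scoring higher on these items and plans t-tests, so score or 0/1 coding fits the plan.

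**Conclusion.** The point holds as an optional efficiency improvement of low severity. Three Aim 2 constructs are measured before randomisation and the planned comparison does not use them. At 30 per arm the standard error would fall by roughly 1-3% at a latent correlation of 0.3, 4-10% at 0.5 and 10-22% at 0.7, depending on the response format, against a cost of about 1% if baseline is uninformative. For a five-category item at 0.5, that is the precision of about 37 women per arm instead of 30.

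These sizes rest on assumed correlations, formats and a 0.5 SD shift, on equal correlation in both arms, and on matching items. Even adjusted, 30-35 per arm detects only medium to large differences, so estimates with intervals matter more than p-values.

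**What to change.** In Section 7, Aim 2, add for knowledge, satisfaction and communication, wherever the baseline and 3-month items match:

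> The arm difference will be estimated by linear regression of the 3-month score (or 0/1 outcome) on arm and the baseline value of the same measure, coded the same way at both times, with one baseline covariate per model. The adjusted mean or risk difference will be reported with its 95% confidence interval.

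Keep the chi-square and t-tests as supportive, and use them alone where items do not match. Leave PCP visit scheduling unadjusted. State how each categorical item is coded, after comparing the two survey forms.

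One wording point should be settled at the same time: Sources of Materials in Section 8 describes follow-up survey data for intervention participants only, whereas Sections 4.4, 4.4.3 and 5 say both arms.

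**Cost.** Two or three sentences, a few lines of code and no new data. Section 5, Aim 1A, anticipates incomplete surveys ("We will also assess the proportion of those successfully recruited who complete the baseline survey and the follow-up survey"), but women are randomised only after the baseline questionnaire, so the covariate should exist for every randomised woman. The statistical price is one degree of freedom per model. Naming the single covariate in advance also removes later discretion over adjustment.
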